**Protocol outline**

|                               |   |
|-------------------------------|---|
| Title                         | Propranolol versus atenolol for problematic infantile hemangiomas: a randomized clinical trial  |
| Version date                  | July 1, 2017  |
| Research Institutions         | Six separate investigation sties in China   |
| Principle Investigators       | [name], [name]  |
| Purpose                       | Comparing the efficacy and safety of propranolol versus atenolol in patients with problematic infantile hemangiomas.  |
| Design                        | A prospective, multicenter, randomized, controlled, open-label clinical trial.  |
| Subjects                      | Patients with superficial or mixed infantile hemangiomas who require systemic therapy.  |
| Research Duration             | Four years  |
| Methods                       | 
Participants are randomized to receive either propranolol or atenolol for at least 6 months.
 
Participants complete a baseline survey and a survey at 96 weeks of follow-up.
 
The primary outcome measure is the clinical response at week 24.
 
Secondary outcome measures include Hemangioma Activity Score, successful initial response, complete ulceration healing time, quality of life, rebound rate, and response at week 96.
 
Frequency and severity of adverse events will be recorded.
 |
| Expected results and meanings | Evidence supporting the use of atenolol as a first-line treatment of choice in infantile hemangioma.  |

---

#### 4 Acknowledgements

(1) The authors are indebted to:

- The participation of the investigational sites and site investigators.
- All other investigators, participating practitioners, nurses and residents involved in the study.
- All the patients and their parents and guardians who participated in this study.

(2) The authors wish to acknowledge:

-This work was supported by grants from the National Natural Science Foundation of China (Grants Nos. 81400862 and 81401606), the Key Project in the Science & Technology Program of Sichuan Province (Grant No. 2019YFS0322), the Science Foundation for The Excellent Youth Scholars of Sichuan University (Grant No. 2015SU04A15), and the 1·3·5 project for disciplines of excellence-Clinical Research Incubation Project of West China Hospital of Sichuan University (2019HXFH056 and 2020HXFH048). The funding bodies were not involved in the design of the study or the collection, analysis, and interpretation of data or the writing of the manuscript.

-The authors declare that they have no competing interests, either financial or non-financial, that could be perceived as prejudicing the impartiality of the research reported.

-Written informed consent for publication in this study was obtained from the patients' parents. Copies of the signed informed consent forms are available for review by the Journal Editors.

-The datasets used and/or analyzed during the current study are available from the corresponding authors on reasonable request.

-All the authors reviewed the manuscript drafts, trial protocol and supplemental data and approved the final version of the manuscript.

-[name], [name] and [name] were involved in the integrity of the data and ensuring the completeness and fidelity of reporting the trial protocol.

## 5 Study background and rationale

IHs are the most common tumors of childhood and occur in approximately 4% to 5% of infants. In the majority of cases, IHs are self-limited and resolve spontaneously without threat or complications. However, in approximately 10% of patients, the lesions can be disfiguring (e.g., facial involvement), destructive (e.g., ulceration), functionally significant (e.g., visual impairment), or even life-threatening (e.g., airway obstruction).

Currently, propranolol is the preferred treatment for problematic proliferating IHs. Although propranolol is clearly efficacious, rare adverse effects, such as hypoglycemia and bronchial hyperreactivity, may be life-threatening. Nonselective  $\beta$ -adrenergic antagonists, such as propranolol, are competitive antagonists of catecholamines at the  $\beta_1$ - and  $\beta_2$ -adrenergic receptors (ARs).  $\beta_2$ -AR blockade may result in hypoglycemia as a result of decreased glycogenolysis, gluconeogenesis, and lipolysis. Moreover, bronchial hyperreactivity is a direct effect of propranolol that results in bronchospasms due to pulmonic  $\beta_2$ -AR blockade. In addition, the lipophilic nature of propranolol is also important. When given to infants, the long-term effects of propranolol may affect the developing central nervous system (CNS), specifically learning and memory.

A solution to minimize some of the side effects of propranolol may be the use of more selective  $\beta_1$ -AR blockers, such as atenolol, which, at low dosages, have little  $\beta_2$  activity. More importantly, atenolol is a large, hydrophilic compound and may exhibit fewer CNS-related adverse effects (e.g., sleep disturbance and agitation) in the treatment of IHs. Unfortunately, there is a paucity of clinical data comparing the efficacy and safety of propranolol and atenolol.

Several retrospective studies and case reports and two small, prospective trials, including one randomized controlled trial, have demonstrated the efficacy of atenolol in the treatment of IHs. However, it is difficult to compare the efficacy and safety of atenolol treatment with those of propranolol treatment since the majority of the previously conducted studies were fragmented, non-large-scale clinical trials. Furthermore, because of the broad heterogeneity of IH (e.g., superficial, mixed or deep, localized or segmental, and proliferating or involuting), confounding by other pharmacologic exposures (e.g., corticosteroids or cardiovascular agents), and associated complications (e.g., ulceration and/or bleeding), observational and retrospective studies may be unable to definitively establish the clinical utility of  $\beta$ -

---

blockers in IH. Therefore, questions regarding the efficacy and safety of propranolol and atenolol must be answered in large randomized clinical trials, which may represent the only way to overcome selection and ascertainment bias.

---

**6 Overall study design:**

This study is a prospective, multicenter, randomized, controlled, open-label clinical trial comparing propranolol and atenolol for the management of problematic IHs. Only patients who had never received IH-specific treatments and had normal heart, liver and renal functions were included. In both groups, patients were admitted and checked for side effects for 8 hours on day 0 and day 7. The patients were observed for therapeutic effects as outpatients during schedule visits. While comparing the efficacy of medication between propranolol and atenolol, the side effects of both drugs were also monitored.

---

Study Type    Interventional

Study Design    Allocation: Randomized

                  Endpoint Classification: Efficacy/Safety Study

                  Intervention Model: Parallel Assignment

                  Masking: Single Blind (Outcome Assessors)

                  Primary Purpose: Treatment; Efficacy/Safety assessment

---

---

## 7 Approvals and legal aspects

### 7.1 GCP statement

This study was conducted in compliance with Good Clinical Practice of Pharmaceutical Products and the Declaration of Helsinki and in accordance with applicable legal and regulatory requirements.

### 7.2 Ethics approvals

Approval was obtained by the Ethics Committee (Institutional Review Board) of West China Hospital of Sichuan University, the study site of the principal investigator, and by the local institution review boards at each participating site.

### 7.3 Study Registration

The trial has been registered at [www.clinicaltrial.gov](http://www.clinicaltrial.gov) (NCT02342275).

### 7.4 Informed consent

Informed written consent was obtained from the parents (or guardians) before enrolment and after the provision of detailed oral and written information concerning the context of the study and its potential benefit to the child and comprehensive safety aspects. The informed consent process was in accordance with Good Clinical Practice of Pharmaceutical Products, the International Council for Harmonization, the Declaration of Helsinki and local regulatory requirements. A patient information sheet containing background information and information about the safety of the study and its possible benefit was provided prior to obtaining consent for the study.

### 7.5 Confidentiality

The investigators will ensure that the subjects' anonymity is maintained. The medical records will only be reviewed by investigators and will be kept confidential without any identifying information on any study materials. A unique study identification number will be assigned and used on all study materials. On the patient report forms or other documents, participants will be identified not by their names but instead by their assigned identification number. If participant names are included on copies of documents submitted to the principal investigator, the names will be obliterated, and the assigned subject numbers will be added to the documents.

---

## 8 Target disease and subjects

The target disease of this study is problematic IH. Patients who are diagnosed with problematic IH in the Department of Pediatric Surgery, Department of Dermatology, Department of Dermatology, and/or Department of Pediatrics in six separate investigation sites in China are subjects. Only patients who voluntarily consent to participate in the study after the study has been fully explained are subjects of the research.

Volunteer recruitment posters will be released in the hospitals, and patients who volunteer to participate after fully understanding the study are targets.

Before explaining the study and receiving consent, the investigators will explain to the parents or guardian that digital photographs will be used to measure the treatment response.

## **9 Expected duration**

Research duration: 4 years.

Recruitment period: 2 years.

After enrolment, each study subject was followed up for 96 weeks following the start of study treatment.

**10 Eligibility/Inclusion criteria:**

|                             |                               |
|-----------------------------|-------------------------------|
| Ages Eligible for Study:    | Between 5 and 20 weeks of age |
| Sexes Eligible for Study:   | Both                          |
| Accepts Healthy Volunteers: | No                            |

Presenting an infantile hemangioma with the following characteristics:

- (1) Superficial or mixed IHs.
- (2) Proliferating hemangioma lesions impairing function (including vision, eating and hearing), in cosmetically sensitive regions, or with ulceration and/or bleeding.
- (3) The minimum diameter of the lesion was 1.5 cm on the face and 3 cm outside the face (or 1.5 cm if it was ulcerated).
- (4) Consent of parents (or the person with parental authority in families): signed and dated written informed consent.

**11 Exclusion Criteria:**

- (1) Patients contraindicated for the administration of  $\beta$ -blockers, such as those with an allergy or hypersensitivity to propranolol; hypoglycemia ( $<40$  mg/dL); hypotension ( $<50/30$  mmHg); severe bradycardia ( $<80$  bpm); second- to third-grade atrioventricular block; heart failure; bronchial asthma or bronchial obstruction.
- (2) Patients with any acute illness or gastrointestinal diseases, especially one interfering with normal oral intake.
- (4) Patients with inadequate liver function:  
Total bilirubin higher than or equal to  $1.5 \times$  the upper limit of the normal (ULN) for age and alanine aminotransferase and aspartate aminotransferase higher than or equal to  $2.5 \times$  the ULN for age.
- (5) Patients with inadequate renal function:  
Serum creatinine higher than or equal to 0.8 (mg/dL).
- (6) Patients diagnosed with deep IH, congenital hemangioma, Kaposiform hemangioendothelioma, tufted angioma, or other vascular anomalies.
- (7) Patients previously treated with any IH therapies, including corticosteroids, propranolol, atenolol, topical timolol, captopril, itraconazole, imiquimod, vincristine, interferon- $\alpha$ , laser therapy or other treatments.
- (8) Indication for treatment with corticosteroids, captopril, itraconazole, imiquimod, vincristine, interferon- $\alpha$ , sirolimus, or tacrolimus for an indication other than IH.
- (9) Indication for treatment with a beta-blocker for an indication other than IH.
- (10) Patients who received the following drugs within the 1 week before enrollment:  $\beta$ -AR agonists, such as epinephrine, norepinephrine and salbutamol, etc.; or other cardiovascular agents, including but not limited to calcium channel blockers, ACE inhibitors and inotropic agents, etc.
- (11) Patients with an inability to participate in or follow-up during the study treatment and assessment plan.

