## 12 Sample size determination

In this trial, propranolol was used as the control group to evaluate the efficacy and safety of the atenolol group (experimental group). The treatment response after 6 months of medication was used as the key therapeutic index. To calculate the sample size for this trial, we used the following assumptions:

- (1) A 2-sided 0.05 significance level;
- (2) Ratio of the propranolol group: atenolol group = 1:1;
- (3) A statistical power of 90%;
- (4) A 20% dropout rate due to ineligibility;
- (5) A follow-up of at least 96 weeks;
- (6) A 24-month recruitment period; and
- (7) In this trial, the atenolol group's evaluation variables were compared with the propranolol group's evaluation variables to test for noninferiority. The hypotheses are listed below:

-H0: Twenty-four weeks after therapy initiation, compared to the treatment response of propranolol therapy, that of atenolol was inferior; and

-H1: Twenty-four weeks after therapy initiation, compared to the treatment response of propranolol therapy, that of atenolol was non-inferior.

(8) Very limited data are available in the literature that can be used to set hypotheses for atenolol treatment. Existing case studies are mainly based on small single-center experiences. According to previous studies, propranolol's total treatment response is assumed to be 70-100%, and atenolol's total treatment response is assumed to be 70-100%. In addition, assuming that the atenolol on propranolol response rate does not fall by greater than 15%, the noninferiority margin was selected to be -15%.

(9) Assuming the ulceration rate in both groups to be 10%.

(10) A sample size of 180 patients was determined to be required for each group (a total of 360 patients).

[figure not shown]
[figure not shown]
---

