## 15 Pretreatment evaluations

(1) At the initial visit, investigators collected demographic and clinical data. The patients' parents who opted for oral  $\beta$ -blocker therapy provided a thorough medical history (e.g., existence of comorbidities) and family history (e.g., cardiovascular disease).

Acquisition of general information:

- Sex;
- Gestational age;
- Date of birth;
- Age,
- Body weight.

Hemangioma histories were also taken from families, including:

- Age when the hemangioma appeared;
- Changes in the color of the hemangioma; and
- The period during which the hemangioma showed the greatest growth before referral.

(2) In all infants, the following inspections were performed before enrollment:

- Heart rate;
- Blood pressure;
- Blood glucose;
- Full blood count;
- Liver function tests;
- Renal function
- Electrocardiogram (ECG); and
- Echocardiogram.

If cardiovascular abnormalities were detected, the patient were evaluated by pediatric cardiologists to ensure that it would be safe to initiate  $\beta$ -blocker treatment. Echocardiographic findings, such as a false tendon in the left ventricle, a patent ovale, left superior vena cava to the coronary sinus, and small systemic-to-pulmonary arterial collateral vessels, were considered normal variants and are not reported as anomalies.

(3) When patients had more than one IH, detailed information was obtained for the most clinically important hemangioma (typically the largest or most ulcerated lesion). Hemangioma assessments included lesion size, lesion location, stage of growth,

---

morphologic subtypes, depth of involvement, and treatment indication.

(4) According to Chang et al., lesion size was recorded using 'hemispheric' measurement. A soft tape measure was draped over the hemangioma, and the longest diameter and a measurement perpendicular to it were noted to obtain a measurement in cm^2.

(5) Hemangioma lesions were classified by morphologic subtypes:

-Localized: well-defined focal lesions;

-Segmental: a hemangioma involving an anatomic region that was often plaque-like and often measured at >5 cm in diameter; or

-Indeterminate: neither clearly localized nor segmental.

(6) Hemangioma lesions were also be classified by soft-tissue depth:

-Superficial, which was defined as red with little or no evidence of a subcutaneous component;

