**16 Study visits**

Study visits were scheduled at enrolment; at 1, 4, 12, and 24 weeks after treatment; and then every 12 weeks until the end of the study or if there was any specific need after enrolment. Body weight, height, heart rate, blood pressure, blood glucose, full blood count, liver function tests, renal function and ECG were obtained during protocol visits and in-between periods if needed. All adverse events, which were identified by the investigators as at least possibly treatment-related during the 24-week treatment phase, were collected by the investigator. At each visit, the drug will be handed over to the parent/guardian in an amount sufficient to last the interim duration.

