#### ***21.4 Definition of adverse events***

Identified adverse events were coded using the latest version of the Medical Dictionary for Regulatory Activities. Adverse events included suspected adverse drug reactions, other medical experiences, regardless of their relationship with the investigative drugs, such as infections, injury, surgery, accidents, extensions of symptoms or apparently unrelated illness, and significant abnormalities in clinical laboratory values or physical examination findings. These medical conditions relate to the disease under study whose changes during the study are consistent with natural disease progression. Therefore, they are not considered adverse events, but they shall be recorded by the investigators. Medical conditions that were present at baseline shall not be considered adverse events unless worsening occurred.

Blood pressure and heart rate values were compared with age-related reference ranges: hypotension was defined as an SBP less than 50 mmHg and/or a DBP less than 30 mmHg; bradycardia was defined as an HR less than 80 beats per minute (bpm) while awake or less than 60 bpm while asleep.

Intolerable CNS-related adverse effects (e.g., sleep disturbance and agitation) were defined as adverse events that did not disappear or were not relieved after treatment administration was altered (e.g., earlier evening dose or a decrease in daily dose). Sleep disturbance was characterized by difficulty in falling sleep and/or remaining sleep, or development of increased waking or night terrors. Agitation was characterized by a state of restlessness associated with unpleasant feeling of irritability and tension.

Bronchial irritation was classified as hyperreactivity, bronchospasm, bronchiolitis, and cold-induced wheezing.

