## ***21.6 Grade of adverse events***

Grade referred to the severity of the adverse event. CTCAE v4.0 displays grades 1 through 5 with unique clinical descriptions of severity for each adverse event based on the general guidelines. A serious adverse event is defined as any of the following toxicities identified during the 6 months of treatment:

- Grade  $\geq 3$  of any adverse events;
- Persistent hypotension;
- Persistent bradycardia; and
- Intolerable CNS-related adverse effects.

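### Exclusion item (4) joins bilirubin, ALT and AST only with 'and', so read literally it admits an infant with markedly raised transaminases and normal bilirubin, contrary to Section 6

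*Combined protocol and SAP*

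**What the plan says.** Section 11 (Exclusion Criteria), item (4), excludes infants with inadequate liver function. It defines this as total bilirubin at or above 1.5 times "the upper limit of the normal (ULN) for age and alanine aminotransferase and aspartate aminotransferase higher than or equal to" 2.5 times the ULN for age. The item contains no 'or', no 'and/or' and no phrase meaning any one of these.

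Section 6 (Overall study design) describes the population differently: "Only patients who had never received IH-specific treatments and had normal heart, liver and renal functions were included".

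The inclusion list in Section 10 has no liver criterion, and no other section gives a liver limit. Liver function tests are on the pretreatment list in Section 15, which opens "In all infants, the following inspections were performed before enrollment". They are repeated later: Section 16 says that "liver function tests, renal function and ECG were obtained during protocol visits".

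Section 25.3 limits the per-protocol analysis to patients who met every inclusion and exclusion criterion.

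**The concern.** Taken as written, item (4) needs three abnormal results before an infant is kept out. An infant with ALT at 10 times the ULN, normal AST and normal bilirubin passes. So does one with both transaminases far above 2.5 times the ULN and normal bilirubin. Neither has the normal liver function that Section 6 describes.

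Two things are at stake. The first is entry: this is the operative liver rule for infants aged 5 to 20 weeks starting an oral beta-blocker, and six sites have to apply it from the text. Section 15 sends cardiovascular abnormalities to a pediatric cardiologist before treatment starts, but provides no matching review for abnormal liver tests. The second is the per-protocol set. An infant with an isolated raised ALT is a valid per-protocol patient under one reading of item (4) and an eligibility violation under the other. In a noninferiority trial, membership of that set should not depend on how a connector is read.

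**Working it through.** No stated figure has to be reproduced. The check is of the logic of the rule.

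**Inputs (Section 11, item (4)).** Three yes/no tests: bilirubin at or above 1.5 × ULN, ALT at or above 2.5 × ULN, AST at or above 2.5 × ULN. They give 2 × 2 × 2 = 8 patterns, of which 8 − 1 = 7 have at least one value over its limit.

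**Three candidate rules.**

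| Values over limit | All three needed (literal) | Bilirubin, or both ALT and AST | Any one value |
|---|---|---|---|
| None | enters | enters | enters |
| Bilirubin only | enters | excluded | excluded |
| ALT only | enters | enters | excluded |
| AST only | enters | enters | excluded |
| Bilirubin and ALT | enters | excluded | excluded |
| Bilirubin and AST | enters | excluded | excluded |
| ALT and AST | enters | excluded | excluded |
| All three | excluded | excluded | excluded |
| **Excluded, of the 7** | **1** | **5** | **7** |

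The literal rule and the any-one-value rule disagree on 7 − 1 = 6 patterns: three with one raised value and three with two. The middle column shows what happens if only the first 'and' becomes 'or': an isolated raised ALT or AST still gets in. Both connectors therefore have to change.

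These are counts of patterns. They say nothing about how often each occurs.

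**Number of infants.** The documents give no frequency, so this is an assumption shown as a range. Let f be the share of the 360 planned infants (Section 12) with one or two values over the limit. The number classified differently is 360 × f:
- f = 0%: 0
- f = 1%: 3.6, about 4
- f = 2%: 7.2, about 7
- f = 5%: 18

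**Does any-one-value wording make Section 6 true?** Not entirely. Bilirubin at 1.4 × ULN or ALT at 2.4 × ULN is above normal but below its limit, so that infant stays eligible. Section 6 therefore needs a small change as well.

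**Primary analysis.** Item (4) acts before randomization, so it bears on both arms alike. Sections 19 and 25.3 define the primary population by randomization, dosing and evaluation, without reference to item (4).

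**The case against.** The strongest reply is that this is loose drafting and that the document as a whole points one way. Item (4) is headed as inadequate liver function, and Section 6 asks for normal function. Section 20.5 joins two exclusions from the rebound analysis with a bare 'and', although either one plainly excludes. Item (1) of Section 11 writes its hypotension limit as a pair of pressures with no connector at all. Item (2), on acute illness, would catch some of these infants. Section 5 names hypoglycemia, bronchial hyperreactivity and central nervous system effects as the drug risks and mentions no liver risk. Liver tests are repeated during follow-up.

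Most of this stands. It makes any one value the probable intent and keeps the point small. It does not remove the defect: item (2) sets no liver limit, repeat tests come after entry, and no other section says which reading of item (4) governs.

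A reader might also infer that requiring all three values was deliberate, because Section 21.4 is explicit where two measurements are involved: "hypotension was defined as an SBP less than 50 mmHg and/or a DBP less than 30 mmHg". The documents do not support that. It is an adverse-event definition, and the eligibility section states the same limits without any connector. With the bare 'and' in Section 20.5, this shows that connectors are not used consistently enough to prove intent.

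**Conclusion.** The point holds as a defect in the wording of a safety entry rule. Read literally, item (4) excludes 1 of the 7 patterns with a raised value and gives a result contrary to Section 6. This rests on taking the item as written; what was meant is probably any one value.

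A reader might go further and infer that infants with abnormal liver function were enrolled, that sites applied the rule differently, or that the efficacy comparison is compromised. The documents show none of these. The number affected is unknown and may be zero, the range of 0 to 18 above is assumed, and no direction between the arms is shown. The primary intention-to-treat analysis and its precision are not materially affected. What remains open is who may enter and who counts as an eligibility violation in the per-protocol set. The rule should be corrected; confidence is medium, because the intent is not stated.

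**What to change.** 1. Reword Section 11, item (4), to: 'total bilirubin ≥ 1.5 × ULN for age, or ALT ≥ 2.5 × ULN for age, or AST ≥ 2.5 × ULN for age'.
2. Use the same rule in Section 25.3 when identifying eligibility violations for the per-protocol set.
3. In Section 6, replace the statement on normal liver function with a reference to the limits, for example 'adequate liver function as defined in Section 11', because mildly raised values remain eligible.

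Much of the text is in the past tense. If enrolment has closed, the sponsor can still state which rule the sites applied and use it consistently for the per-protocol set.

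The cost is one sentence in item (4), one clause in Section 6 and a cross-reference in Section 25.3. No new tests are needed, since liver function is already measured before enrolment. The downside is possibly a few more screen failures.
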